2.2 TRIAL OBJECTIVES

The overall purpose of this open label extension (OLE) trial is to assess long-term safety and efficacy (durability of response) of BI 655066 in patients with moderate to severe chronic plaque psoriasis. In addition, this study will provide an opportunity for subjects to have extended access to a proven active therapy for approximately four years administration.

The primary objective of the study is to investigate safety of BI 655066, in patients with moderate to severe chronic plaque psoriasis, receiving long-term treatment.

Additional objectives of this study are to further investigate long-term efficacy, tolerability, pharmacokinetics, pharmacodynamics and immunogenicity of BI 655066.

Study endpoints are listed in [Section 5](#).

2.3 BENEFIT - RISK ASSESSMENT

Results of the Phase I study with BI 655066 (study 1311.1) suggest that a single injection intravenously or subcutaneously (i.v. or s.c.) of BI 655066 is associated with substantial and durable improvements in the cutaneous manifestations of psoriasis. At doses of 0.25 mg/kg intravenously and above, all active dose groups showed improvement in mean PASI scores of at least 75% from baseline by week 12, which lasted at least until week 24. Similar improvements were observed in both of the active BI 655066 subcutaneous dose groups ([M14-0004](#)).

Patients rolling over in this OLE will have completed the single blind 1311.2 study where 75% of all patients will have received BI 655066 at different dose levels. Based on the preliminary data from study 1311.1 described in [Section 1.2](#), where good tolerability was

Proprietary confidential information.

© 2018 Boehringer Ingelheim International GmbH or one or more of its affiliated companies. All rights reserved.

This document may not - in full or in part - be passed on, reproduced, published or otherwise used without prior written permission.

shown, and no drug related serious adverse events (SAE), patients are likely to benefit from participation in this study.

Risks of participating in this study include risks related to the trial specific procedures such as blood sampling, subcutaneous injection of study medication. Blood sampling and subcutaneous injections can cause local bruising, inflammation, and pain.

As with any immune modulating agent, BI 655066 has the potential to impair immune function resulting in a risk of infection. This will be addressed by clinical monitoring for AEs during the treatment and follow up periods. Interferon gamma (IFN- γ) release assay to *M. tuberculosis* will be obtained at the initial roll-over visit, in order to exclude or discontinue documented untreated patients with active or latent tuberculosis infection (TB). All patients will be re-tested at the Extended end of treatment visit in order to assess long-term impact of BI 655066 on *M. tuberculosis* exposure. Patients having current signs or symptoms of infection or history of serious infection will not be included in the study.

The role of IL-23 in tumour immunity is not well established at this time, but an increased risk of cancer from an IL-23 antagonist, though considered small, cannot be excluded.

Major adverse cardiovascular events (MACE), including myocardial infarction, cerebrovascular accident, and cardiovascular death, have been initially reported in association with the anti-IL-12/23 agents, ustekinumab and briakinumab, in patients with psoriasis. However, such a risk has not been confirmed among patients receiving ustekinumab for up to five years ([R13-3518](#)). The overall risk of MACE in the present study is considered to be low.

Local reactions to i.v. and s.c. administered biologic agents are uncommon, and are usually limited to redness, swelling or induration at the injection site. Manifestations of systemic hypersensitivity reactions include anaphylaxis, pruritus, hypotension, and respiratory distress. Both local and systemic hypersensitivity reactions are readily detectable, transient in nature, and manageable with standard medical treatment. No systemic hypersensitivity reactions have been reported with BI 655066 to date. Patients will be closely monitored 30 minutes to 1 hour after drug administration for signs of redness, swelling or hardness at the injection site or generalized itching, dizziness or difficulty breathing.

Although rare, a potential for drug-induced liver injury is under constant surveillance by sponsors and regulators. Therefore, this study requires timely detection, evaluation, and follow-up of laboratory alterations of selected liver laboratory parameters to ensure patients' safety (cf. [section 10.4](#)).

The study has been designed, and will be conducted in such a manner as to limit these risks as much as possible. In order to mitigate any safety signals as early as possible, an independent Data Monitoring Committee (DMC) will oversee this study. Since all patients will receive active treatment at a dose of, or greater than the projected marketed dose, most patients will likely have a benefit from participating in this study. Therefore, the benefit-risk assessment is considered appropriate for a clinical trial of an experimental therapy at this stage of development.

Proprietary confidential information.

© 2018 Boehringer Ingelheim International GmbH or one or more of its affiliated companies. All rights reserved.

This document may not - in full or in part - be passed on, reproduced, published or otherwise used without prior written permission.

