4.1.2 Method of assigning patients to treatment groups

Patients will receive a single dose of open label BI 655066 every 12 weeks. The initial dose for all patients moving into the open label extension study will be 90 mg.

If response is maintained, i.e. achievement of PASI₉₀ at Extended visit 2, 90 mg dosing will occur every 12 weeks until Extended EOT.

If there is a lack of response, defined as response below PASI₉₀ at Extended visit 2, the dose should be increased to 180 mg, and the 180 mg dosing will occur every 12 weeks until Extended EOT.

Detailed instructions for preparation of BI 655066 for administration of each dose will be given in the ISF.

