4.1.3 Selection of doses in the trial

The treatment is derived from the treatment groups in the preceding phase II trial, where the dose selection is based on the completed phase I trial in which clinical improvement in patients with psoriasis was observed across a wide dose range (~18 mg -375 mg).

The choice of the “90 mg/dose” was based on several pieces of data obtained in the initial 1311.1 single-dose, dose-escalation study: an analysis of dose given (and the subsequent “area under the curve” exposure data) plotted against the clinical response based on the PASI

Proprietary confidential information.

© 2018 Boehringer Ingelheim International GmbH or one or more of its affiliated companies. All rights reserved.

This document may not - in full or in part - be passed on, reproduced, published or otherwise used without prior written permission.

score noted that the stable effective dose was likely to be greater than 1.0 mg/kg (approximately 90 mg)

Subsequent to selection of the starting dose for 1311.13, an interim analysis of 1311.2 indicated that the 180 mg dose resulted in a numerically higher proportion of patients who achieved PASI90. Since the higher dose was not associated with a higher incidence of any specific adverse events, patients who do not achieve PASI90 on the 90 mg dose are eligible to receive the higher dose of 180 mg. This dose is also consistent with the objective of obtaining safety data on a dose equal to or greater than the proposed “to be marketed” dose of 150 mg, allowing us to obtain additional safety information appropriate for inclusion in future discussion with health authorities.

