- Inclusion criteria 3 (Negative serum β -Human Chorionic Gonadotropin (β -HCG))
Exclusion criteria 8 (Any clinically significant laboratory abnormalities)

Check consistency in medical history with the data obtained at visit 1 of the previous trial. All changes in medical history must be documented as adverse events and will be followed up as such during this trial.

Re-record ongoing adverse events/concomitant medications from the previous trial and record any adverse events/concomitant medications that may have started between the two trials, in the event that the 6 week time-window between trials was used.

All patients will be administered 90 mg BI 655066 s.c. at Extended visit 1.

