6.2.3 End of trial and Extended follow-up period

Trial 1311.13 is an open label extension trial which was set up in order to assess the long term safety and efficacy of Risankizumab (BI 655066) in patients with plaque psoriasis who have completed the phase 2 trial 1311.2. Moreover, this trial was meant to offer patients continuous treatment with Risankizumab until the marketing approval and availability of Risankizumab in the respective participating countries.

In the course of the acquisition of Risankizumab by Abbvie and the transition of responsibilities from BI to Abbvie it is planned to transfer the patients who are treated in 1311.13 into M15-997 which is sponsored and conducted by Abbvie. M15-997 is an open label extension trial in which patients who have completed one of the Risankizumab pivotal trials in the indication of plaque psoriasis receive 150 mg Risankizumab every 12 weeks.

For patients who discontinue study medication before Extended end of treatment (for any reason), or before approval of this amendment and start to rollover patients to the M15-997 from 01-May-2018 an early Extended EOT visit should be scheduled. If the decision to discontinue study participation is taken at a regular study visit, the visit should be turned into an Extended EOT visit. If the decision to discontinue study participation is taken in between study visits, an Extended EOT visit is to be scheduled at the earliest convenience and by the latest at the next upcoming visit according to the Flow Chart. This early Extended EOT visit will include the same procedures as the normal EOT, and the patient will subsequently enter a follow up period of 12 weeks, until a final Extended EOS visit is performed. If the decision to discontinue is taken in the Extended follow up period, the Extended EOS visit is to be scheduled at the earliest convenience. The procedures described at Extended EOS will be performed and the information will be recorded in the CRFs.

The end of study procedures are listed in [Flow Chart](#).

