### **11.2 Analysis of Adverse Events**

#### **11.2.1 Treatment Emergent Adverse Events**

Treatment emergent adverse events (TEAEs) are defined as any event with an onset that is after the first dose of risankizumab in this study and with an onset date within 105 days after the last dose of study drug in the analysis period.

Events where the onset date is the same as the study drug start date are assumed to be treatment emergent, unless the adverse event start time is prior to the study drug start time. If an incomplete onset date is collected for an adverse event, the event will be assumed to be treatment-emergent unless there is other evidence that confirms that the event is not treatment-emergent (e.g., the event end date is prior to the study drug start date).

The number and percentage of subjects experiencing treatment-emergent TEAEs will be tabulated using the Medical Dictionary for Drug Regulatory Activities (MedDRA®) system organ class and preferred term.

Considering the fact that some subjects had dose escalation due to lack of efficacy at EV2, selected safety tables will be generated breaking down by the group of subjects who remained at 90 mg throughout the study, the group of subjects who received 180 mg at EV2, and total.

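### Protocol 2.3 says every patient receives at least the projected marketed dose, but all start at 60% of it; separately, the SAP's 180 mg safety group includes events that began on 90 mg

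*Protocol*

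**What the plan says.** **Dose.** The closing paragraph of Protocol 2.3 rests the expected benefit on this premise: "Since all patients will receive active treatment at a dose of, or greater than the projected marketed dose". Section 4.1.3 gives the proposed marketed dose as a "dose of 150 mg, allowing us to obtain additional safety information". Section 6.2.3 says that patients in the follow-on study "receive 150 mg Risankizumab every 12 weeks".

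Section 4.1.2 sets the dosing in this trial: "The initial dose for all patients moving into the open label extension study will be 90 mg". Section 6.2.2.1 repeats it: "All patients will be administered 90 mg BI 655066 s.c. at Extended visit 1". For patients with PASI90 at EV2, "90 mg dosing will occur every 12 weeks until Extended EOT". Patients below PASI90 at EV2 go to 180 mg every 12 weeks.

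**Safety tables.** SAP 11.2.1 defines a treatment-emergent event as one "with an onset that is after the first dose of risankizumab in this study" and within 105 days after the last dose. Because some patients escalate at EV2, it breaks selected safety tables into "the group of subjects who remained at 90 mg throughout the study", those who received 180 mg at EV2, and the total. In the overall total each patient is counted once. The event-rate denominator runs from first to last dose plus 105 days and is not divided by dose.

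**The concern.** The two parts are independent and should be judged separately.

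The first is a factual contradiction in current protocol text. Section 2.3 is what an ethics committee reads on benefit and risk, and its conclusion follows directly from the incorrect sentence.

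The second concerns what the SAP's only safety breakdown by dose can show. Safety is the primary objective (Protocol 2.2), and section 4.1.3 justifies the 180 mg option partly by the wish for safety data at or above 150 mg. Only time on 180 mg supplies such data. The SAP forms the group from something that happens at EV2, yet credits it with events from before EV2. Patients who stop before EV2, including for adverse events, can never enter it. SAP 9.0 counts patients by dose at each visit and 11.2.2 lists SAEs, deaths and discontinuations for adverse events, but no planned table gives event counts or rates by dose at onset.

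**Working it through.** The trial tests no hypothesis and has no sample size calculation, so there is no stated figure to reproduce.

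**1. Dose against the premise**
- 90 / 150 = 0.60; 180 / 150 = 1.20.
- From EV1 to EV2 no patient is at or above 150 mg. After EV2, PASI90 responders remain below it and only escalated patients exceed it.

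**2. Time on 90 mg inside the 180 mg group**
- EV2 is scheduled at 12 weeks (84 days) with a window of ±7 days (Protocol flow chart), so 77 to 91 days.
- 77 / 365.25 = 0.21, 84 / 365.25 = 0.23 and 91 / 365.25 = 0.25 patient-years per escalated patient.
- The number escalated is not given. For 25, 50 or 75 patients (assumption), at 84 days: 5.7, 11.5 or 17.2 patient-years.

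**3. Share of an escalated patient's time**

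The denominator is last dose − first dose + 105 days (SAP 11.2.1, item 4), taking the first dose as the one in this study, with no earlier dosing in this trial.
- Last dose week 48: 84 / (336 + 105) = 84 / 441 = 19.0%.
- Last dose week 144: 84 / (1008 + 105) = 84 / 1113 = 7.5%.

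Week 144 is a realistic upper end. The amendment that introduced the Extended period is dated 10 June 2015, and the switch to a final visit applies after 1 May 2018. That is 1056 days, or 150.9 weeks, so week 144 is the latest 12-weekly dose if EV1 fell on the amendment date and the last amendment was approved locally by 1 May 2018.

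**4. Effect on the any-AE percentage**

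A patient is wrongly shown as a case only with an event before EV2 and none afterwards. At an assumed constant rate r per patient-year, with t₁ = 84 / 365.25 = 0.230 years before the first 180 mg dose and t₂ years after it, the proportion is (1 − exp(−r·t₁)) × exp(−r·t₂). For week 48, t₂ = 357 / 365.25 = 0.977; for week 144, t₂ = 1029 / 365.25 = 2.817.

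| r | Event before first 180 mg dose | and none after, last dose week 48 | and none after, last dose week 144 |
|---|---|---|---|
| 0.5 | 10.9% | 6.7% | 2.7% |
| 1 | 20.5% | 7.7% | 1.2% |
| 2 | 36.9% | 5.2% | 0.1% |

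These are percentages of escalated patients. The rates are assumptions; the documents give none.

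**5. Rarer events**

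As r becomes small, the share of the column's cases that arose only before 180 mg tends to t₁ / (t₁ + t₂). That is the time share in step 3, 7.5% to 19.0%. For SAEs or AESIs this is the relevant scale.

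**The case against.** Most of the case for leaving the plan alone is sound on consequence.

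- The sentence in 2.3 drives nothing else. The dosing instructions are correct, 4.1.3 openly states both 150 mg and the 90 mg rationale, and 2.3 separately supports benefit from the Phase I data. This version is dated 30 January 2018 and the trial closes soon after 1 May 2018, so few patients gain from a correction. All of this stands; the sentence is still wrong.
- The primary safety analysis is overall incidence (Protocol 7.3.1), which the total column gives without distortion. The SAP describes groups of patients and does not call the second column a rate on 180 mg. Any rates split this way would be internally consistent, because events and time cover the same period. This stands too, but the SAP gives dose escalation as the reason for the split, so readers will take the columns as doses.
- The tables to be split are not named, it is not stated whether the rate tables are among them, and the phrase about the analysis period in the event definition is undefined. That wording does not create a window starting at the first 180 mg dose.

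A reader might infer more than the documents support:

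- *That 11%, 21% or 37% of the escalated group is misclassified.* Those are patients with any event before 180 mg. Most would also have one afterwards and be counted anyway; step 4 gives the actual shift.
- *That 84 days is a minimum.* The visit window allows 77.
- *That Pre-Extended dosing typically lifts the 90 mg share to 25% or 31%.* Such figures need 36 to 48 earlier weeks on 90 mg with no gap. Dosing was then capped at one year from the first dose in either trial (Protocol section 11, amendment 1), and about 75% had already received the drug in 1311.2. Long earlier dosing would apply to few patients, mainly former comparator patients.

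**Conclusion.** Both parts hold, at moderate weight.

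The 2.3 premise is incorrect: 90 mg is 60% of the proposed dose, nobody meets the premise before EV2, and PASI90 responders at EV2 never do. It does not follow that patients are inadequately treated or that benefit is unsupported, since the 90 mg rationale and Phase I data are separate grounds.

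The SAP's 180 mg group is not a record of safety on 180 mg. Each member brings 0.21 to 0.25 patient-years on 90 mg, plus any Pre-Extended dosing. The shift in the any-AE percentage is small with long follow-up (0.1 to 2.7 points at week 144) and modest with short follow-up (5 to 8 points at week 48). For rarer events the misattributed share of cases approaches 7.5% to 19%, and is larger for patients dosed in the Pre-Extended period. These sizes assume constant event rates of 0.5 to 2 per patient-year for the any-AE figures, and no earlier dosing in this trial. The overall safety result is unaffected.

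**What to change.** **Protocol 2.3.** Replace the sentence: all patients start on 90 mg, below the proposed 150 mg, and only EV2 non-responders are raised above it, to 180 mg. Rest the expected benefit on the 90 mg rationale and the Phase I data. Section 4.1.3 needs no change.

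**SAP 11.2.1.** Keep the planned patient-level split and the total; the split remains useful for long-latency events such as malignancy. Name the tables it covers. Add descriptive AE, SAE and AESI counts and exposure-adjusted rates by dose received at onset, counting events and person-time before the first 180 mg dose as 90 mg. Label these tables non-randomised.

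**Cost.** The protocol change needs amendment approval (section 8.1) and leaves a slightly less favourable benefit statement. The SAP change is a few extra tables from dose and onset dates already collected, and can be prespecified because the SAP is to be signed before database lock. The 180 mg columns will be sparse and drawn only from EV2 non-responders who stayed on treatment to EV2, so they describe safety on 180 mg and do not support a comparison of doses.

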3. DESCRIPTION OF DESIGN AND TRIAL POPULATION

3.1 OVERALL TRIAL DESIGN AND PLAN

This open label extension trial (OLE), investigates the additional safety and efficacy of the 90 mg dose of BI 655066. Approximately 100 patients who meet the entry criteria are planned for inclusion in this trial, rolling over from the preceding 1311.2 trial. The treatment will be open label.

The treatment period will be approximately four years of administration starting with first administration of BI 655066 in either trial 1311.2 or 1311.13, followed by a 12 week follow up period. After 01-May-2018 and approval of this protocol amendment in each respective country, the next study visit will be the Extended EOS visit and therewith the last visit in this study. Patients who have completed the study without early treatment discontinuation will be offered to roll over to M15-997 open label extension (OLE) trial if they fulfill the in- and exclusion criteria for the M15-997 trial. Refer to [section 6.2.3](#).

Patients rolling over from the preceding trial 1311.2 will have to complete the treatment period in that trial, or complete the entire trial including the follow up period, reaching end of study. If, during the follow up period of the preceding trial (at any visit from week 24 and onwards in trial 1311.2) loss of response is detected, the patient can roll over in this extension trial. For this, loss of response is defined as $< \text{PASI}_{50}$.

Extended visit 1 of this trial should preferably be performed as a combined visit the same day as End of Study visit of 1311.2, or within an interim period of maximum 6 weeks thereafter.

1311.2

[figure not shown]
[figure not shown]

Figure 3.1:1 Guideline for roll over of patients from 1311.2 to OLE study 1311.13

After the approval of this protocol amendment in each respective country, all patients will follow [Flow Chart](#) (Extended Dosing Period) and receive 90mg BI 655066 subcutaneously at their Extended visit 1 (EV1). From EV1 onwards, BI655066 will be administered subcutaneously every 12 weeks during the trial. At EV2, if there is a lack of response, defined as <PASI90, the dose should be increased to 180mg for the remainder of the trial (see Fig 3.1.2).

For ongoing patients under the previous protocol amendment (Pre-Extended Dosing Period, [see Fig 3.1.3](#)), EV1 should be conducted at the following time points:

1. For ongoing patients with ≥ 12 weeks since the EOT visit: Conduct EV1 as soon as possible
2. For ongoing patients still undergoing treatment or with <12 weeks since the EOT visit: Conduct EV1 at the time of the next scheduled treatment or follow up visit (note: EV1 should not be conducted at the time point of Visit 2 under the previous protocol, patients with Visit 2 as their next scheduled visit should have their EV1 replacing their Visit 3 instead)

* EV stands for extended visit

** Week 0 is the first scheduled visit after amendment approval.

1

Figure 3.1:2 Guideline for assessment of dose adjustment

Visit	Treatment period							Follow Up period			
	1 ¹	2	3	Interim Contact	4	5	EOT	FU 1	FU 2	FU 3	EOS visit
Day	1	42	84	126, 210, 294, etc...	168	252	336		EOT +168	EOT +252	EOT +336
Week	0	6	12	18,30, 42, etc...	24	36	48	EOT +12	EOT +24	EOT +36	EOT +48
Visit window (days)	+7	±7	±7	±7	±7	±7	±7	±7	±7	±7	±7

Figure 3.1:3 Visit schedule Pre-Extended Dosing Period

If there are any tolerability issues, as assessed by the investigator, the patient will be discontinued.

The plaque psoriasis will be evaluated by PASI score at each visit. The standard clinical endpoints of PASI50, PASI75, PASI90 and PASI100 will be assessed at each visit based on the baseline PASI from 1311.2.

The end of study is defined as the date the last subject completes the Extended End-of-study visit.

